## EQ VAS

The EQ visual analogue scale (EQ VAS) records the subject's self-rated health on a vertical, visual analogue scale (VAS).

The subject responses to EQ VAS scores (continuous) will be summarized at all study visits. The change in EQ VAS score between baseline and all post-baseline study visits will also be summarised.

# Statistical Analysis Plan

A Multi-center Outcomes Clinical Study of the PyroTITAN™ HRA Shoulder Implant in Humeral Head Resurfacing

Number: CP-HRA-002  
ST: ST1159  
Version: 1.0 05/Oct/2023  
Page: 18 of 19

EQ VAS will be assessed using repeated measures ANCOVA model, with the change from baseline in EQ VAS as the dependent variable. As a minimum the model will contain terms for visit (repeated term) and baseline EQ VAS. The following terms will be added to the model using a stepwise selection procedure with an F-value to attain a significance level of 0.1: site, primary diagnosis and BMI. The p-value for the type III effects of all fixed effects terms included in the final model will be presented. The Least Square Mean (LSMean) change in EQ VAS between baseline and all post-baseline study visits will be presented with the associated 95% confidence interval and p-value.

If the data does not satisfy the assumptions of an ANCOVA model then an appropriate non-parametric analysis will be considered such as Wilcoxon Signed Rank Test, with the Hodges-Lehmann estimate of the median change in EQ VAS presented along with the associated 95% confidence interval.

## Radiographic success (X-Ray and MRI)

Radiographic analysis will be performed by a third-party vendor (Medial Metrics Inc.) under a separate SAP.

## 7.11 Analysis of Exploratory Endpoint(s)

### Range of Motion

Summary statistics for both passive and active range of motion on the operative shoulder will be given as continuous variables for:

- Forward elevation
- External rotation (Arm comfortably at side)
- External rotation (Arm at 90° abduction)
- Internal rotation (Highest posterior anatomy reached with thumb)
- Internal rotation (Arm in abduction)
- Cross-body adduction (Antecubital fossa to opposite acromion)
- Abduction

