## **7.0 Revision/Re-operation**

---

Post-operative surgical procedures associated with the operative shoulder are categorized as Adverse Events. If a Subject undergoes any surgical procedure on the operative shoulder in which all of the original Pyro-Titan Resurfacing Shoulder implant components are retained (debridement etc), the Subject is not withdrawn from the study and all follow-up visits are maintained according to the Subject Management Schedule. If the Pyro-Titan Resurfacing Shoulder prosthesis implant is removed then the Subject is considered revised, is withdrawn from the study, an Adverse Event and Study Completion CRFs must

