## **11.3 Sample Size and Power Analysis**

The original sample size in this study was 150 enrolled subjects. Additional proof testing and improvements in the device inspection process were employed during the study, at which time it was determined that an additional cohort of subjects was necessary. We are now comparing a cohort of subjects enrolled after these changes to the original cohort of subjects.

With an expected attrition rate of 10% per annum, this will yield an evaluable sample size of 52 shoulders at ten years ( $150 * 0.9^{10} = 52.3$ , where 0.9 or 90% is the number expected to be retained from one year to the next). Based on past experience, we may obtain clinical follow-up on this number of shoulders, but we may obtain radiographic follow-up on as few as two-thirds of these shoulders (about 35 shoulders). This remaining number of evaluable shoulders with clinical and radiographic follow-up is adequate to establish a reliable ten-year survival estimate of survival for hemi arthroplasty (Dorey and Amstutz, 1986).

For the new cohort, the sample size is calculated based on the non-inferiority of the study device. The success rate for the study device is 96.1% from the original population and is used as reference rate. Therefore, for a conservative success rate of 96.1% of the study device is used in the study. The non-inferiority margin  $\delta$  of -0.033 is chosen in the study. 212 subjects are required to achieve  $100(1 - \beta) \% = 80\%$  power to detect non-inferiority at the Significance level of  $\alpha = 0.05$ . To account for 10% lost to follow-up, the

total number of additional subjects is 237. Therefore, the estimated enrollment for the study will be 387 subjects.

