### **11.9 Other Endpoints**

The following will be analyzed at the end of the trial:

Adverse Events including, but not limited to:

- Infection
- Loss of fixation
- Breakage
- Dislocations
- Revisions

Data will be entered, verified and validated using a computer database system. Both the data management and statistical analysis will be performed by Ascension Orthopedics, Inc. Descriptive statistics of patient demographic details will be calculated over all patients. Pre-operative values of outcome variables will be compared to postoperative values at various time points. For interval level data, t-tests will be used; for ordinal level data (ranked data) the Wilcoxon matched-pairs signed-ranks test will be employed, and chi-square or Fisher's exact tests will be used for categorical data. Correlation coefficients may also be employed to determine whether preoperative variables are related to outcome variables.

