### 5.3 Exploratory Endpoint(s)

To demonstrate postoperative functionality at 2, 3, 4, 5, 8 and 10 years post treatment, as compared with pre-treatment results through:

- Range of motion

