## 7.3 Handling of Missing, Incomplete and Repeat Data

Data will be analysed as observed in the study database.

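### SAP 5.3 defines range of motion as a comparison with pre-treatment, but SAP 7.11 plans only summary statistics and no change from baseline (minor; exploratory endpoint)

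*SAP*

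**What the plan says.** SAP 5.3 states the endpoint as: "To demonstrate postoperative functionality at 2, 3, 4, 5, 8 and 10 years post treatment, as compared with pre-treatment results through" range of motion. Protocol 11.9 has a general rule in the same direction: "Pre-operative values of outcome variables will be compared to postoperative values at various time points", with t-tests for interval data and the Wilcoxon matched-pairs test for ordinal data.

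The analysis in SAP 7.11 is "Summary statistics for both passive and active range of motion on the operative shoulder will be given as continuous variables" for seven measures. It names no visits, change score, interval or test. SAP 7.1 defines summaries of continuous variables as number of observations, mean, median, standard deviation, minimum and maximum.

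SAP 7.4 derives change from baseline for VAS, ASES, WOOS, Constant-Murley, EQ-5D and EQ VAS. It has no entry for range of motion. SAP 7.5 leaves baseline data that are reported alongside later visits to the relevant endpoint section, which here is 7.11, and its own baseline lists do not include range of motion.

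On who contributes at each visit, SAP 7.3 says: "Data will be analysed as observed in the study database". Protocol 11.3 says of the original 150: "With an expected attrition rate of 10% per annum, this will yield an evaluable sample size of 52 shoulders at ten years". Under Protocol 7.0, if the prosthesis "is removed then the Subject is considered revised, is withdrawn from the study".

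**The concern.** The endpoint is a contrast with the pre-operative state, and the planned output contains no contrast. Nothing in the SAP presents this as a decision. Where SAP 7.10 drops a change analysis, for VAS satisfaction, it gives the reason (no baseline assessment). No reason is given for range of motion, and SAP 7.14 lists only the 5-year interim analysis as a departure from the protocol.

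Two things are at stake. The stated question goes unanswered. And a reader who wants the answer will subtract one mean from another, when the later mean comes from fewer subjects, not necessarily like those behind the baseline mean. The marginal SDs also do not yield a valid interval for the change, because the within-subject correlation is not reported.

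**Working it through.** **1. Endpoint against analysis.**

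| Element | SAP 5.3 / Protocol 11.9 | SAP 7.4 / 7.11 |
|---|---|---|
| Contrast | Post-operative against pre-operative | None |
| Time points | 2, 3, 4, 5, 8, 10 years (5.3) | None named |
| Change variable | Implied | Not derived |
| Test or interval | t-test or Wilcoxon (11.9) | None |

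**2. Does the Constant score fill the gap?** Only in part. Four motions enter its mobility sub-score (40 of 100 points), and the total does get a change from baseline and a paired test. But flexion and abduction are scored in bands of about 30 degrees (31 and 60 degrees both score 2 points), rotation is scored by hand position or anatomical level, and all four are pooled with pain, daily activities and strength. This gives no change per motion and no split between active and passive.

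**3. Expected retention.** The protocol's own figure reproduces: 150 × 0.9^10 = 52.3, stated as 52. At 10% per year the share remaining is 0.9^2 = 81% at 2 years, 0.9^5 = 59% at 5 years, 0.9^8 = 43% at 8 years and 0.9^10 = 35% at 10 years.

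Two 10-year scenarios for all 387:
- The documents' own mix: 10% per year for the original 150 and 10% total loss for the additional 237. This leaves 52.3 + 0.9 × 237 = 52.3 + 213.3 = about 265, so f = 0.69.
- 10% per year for everyone, which extends the original cohort's rate to the new cohort by assumption: 387 × 0.9^10 = about 135, so f = 0.349.

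**4. Bias of a difference of means.** Let S and L be the mean pre-operative motion of those who stay and those who leave, and f the share who stay. The baseline mean is fS + (1 − f)L. The later mean is S plus the mean change among stayers. Subtracting gives the mean change among stayers plus (1 − f)(S − L). The second term is the bias; a paired change removes it.

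**5. Illustration.** S − L is not in the documents. Assume 5 to 10 degrees:
- f = 0.69: 0.314 × 5 = 1.6; 0.314 × 10 = 3.1 degrees.
- f = 0.349: 0.651 × 5 = 3.3; 0.651 × 10 = 6.5 degrees.

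If leavers had the better motion before surgery, the sign reverses and the gain is understated.

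**The case against.** The strongest case on the other side is that descriptive reporting is legitimate here. Range of motion is labelled exploratory in the SAP, is not in the protocol's endpoint lists, supports no success criterion, and belongs to a study that Protocol 11.1 calls exploratory. Protocol 11.9 still requires pre/post comparison and is not withdrawn, SAP 7.1 allows 95% confidence intervals where appropriate, and the table shells, which are not available here, may contain change columns. All of this stands, and it keeps the point minor. It does not remove it: SAP 5.3 promises a comparison that SAP 7.11 does not specify.

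Four stronger readings are tempting, and the documents do not support them.

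- *The reported gains will be inflated by a known amount.* No range-of-motion SD and no difference between stayers and leavers is given, so both size and sign are assumptions.
- *Pairing will also sharpen the estimate.* Not in general. With equal SDs s, 387 at baseline and 135 at 10 years, the difference of means has variance s²(1/387 + 1/135 − 2r/387) once the overlap is counted and dropout is taken as unrelated to motion: 0.0084s² at r = 0.3 and 0.0074s² at r = 0.5. The paired change has 2s²(1 − r)/135: 0.0104s² and 0.0074s². Pairing is about 23% worse or equal. The case for it is that it compares like with like.
- *Pairing cures dropout.* It does not. Withdrawal on implant removal is a post-operative event, and paired change describes only those still followed.
- *Baseline data certainly exist.* Protocol 6.3 lists range of motion among assessments at the Section 2 intervals, which include the pre-operative visit. But the Section 2 table has no row for it, and the pre-operative lists in Protocol 6.1 and 6.2 do not name it.

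**Conclusion.** The point holds as a mismatch within the SAP, and between the SAP and Protocol 11.9: the endpoint is a comparison with pre-treatment, and no such comparison is planned. This rests on the text alone and needs no assumption. Any bias from comparing means is of unknown size and direction. The figures of 1.6 to 3.1 degrees (about 265 of 387 remaining) and 3.3 to 6.5 degrees (35% remaining) are illustrations that depend on an assumed baseline difference of 5 to 10 degrees in favour of stayers. Severity is minor, because the endpoint is exploratory and no study conclusion depends on it.

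**What to change.** 1. Confirm from the case report forms that pre-operative range of motion was recorded. If it was not, amend SAP 5.3 to a descriptive endpoint; the remaining steps then fall away.
2. Add change from baseline for range of motion to SAP 7.4.
3. In SAP 7.11, for motions measured in degrees, report n, paired mean change and 95% CI at 2, 3, 4, 5, 8 and 10 years, active and passive separately.
4. For measures recorded as an anatomical level, such as internal rotation by thumb reach, use the ordinal paired method of Protocol 11.9 and do not treat them as continuous. Settle the scale of cross-body adduction from the form.
5. Keep the summary statistics, and name the visits they cover.
6. Label the intervals as descriptive and unadjusted, since SAP 7.8 plans no multiplicity adjustment. Five motions in degrees, active and passive, at six times would already give 5 × 2 × 6 = 60 intervals.
7. State that the paired change describes only subjects still in follow-up, and claim no gain in precision.

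The cost is SAP wording, the derived variables and one further table. If baseline values exist, no new data are needed. The drawback is the number of intervals, which the descriptive label addresses.

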## 7.12 Analysis of Safety Endpoint(s)

### Adverse events

The number of events and the number of subjects reporting: adverse events (AEs), serious adverse events (SAEs), adverse device effects (ADEs), serious adverse device effects (SADEs), and unanticipated serious adverse device effects (USADEs) will be summarised.

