# 6 STATISTICAL CONSIDERATIONS

## 6.1 Determination of Sample Size

The following is the sample size justification taken from the study protocol V2, 27-May-2013:

The original sample size in this study was 150 enrolled subjects. Additional proof testing and improvements in the device inspection process were employed during the study, at which time it was determined that an additional cohort of subjects was necessary. We are now comparing a cohort of subjects enrolled after these changes to the original cohort of subjects.

With an expected attrition rate of 10% per annum, this will yield an evaluable sample size of 52 shoulders at ten years ( $150 * 0.9^{10} = 52.3$ , where 0.9 or 90% is the number expected to be retained from one year to the next). Based on past experience, we may obtain clinical follow-up on this number of shoulders, but we may obtain radiographic follow-up on as few as two-thirds of these shoulders (about 35 shoulders). This remaining number of evaluable shoulders with clinical and radiographic follow-up is adequate to establish a reliable ten-year survival estimate of survival for hemi arthroplasty (Dorey and Amstutz, 1986).

For the new cohort, the sample size is calculated based on the non-inferiority of the study device. The success rate for the study device is 96.1% from the original population and is used as reference rate. Therefore, for a conservative success rate of 96.1% of the study device is used in the study. The non-inferiority margin  $\delta$  of -0.033 is chosen in the study. 212 subjects are required to achieve  $100(1 - \beta) \% = 80\%$  power to detect non-inferiority at the Significance level of  $\alpha = 0.05$ . To account for 10% lost to follow-up, the total number of additional subjects is 237. Therefore, the estimated enrolment for the study will be 387 subjects.

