## 6.3 Interim Analysis

A 5-year interim analysis will be carried out for this study.

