# 7 STATISTICAL ANALYSIS

## 7.1 General

Smith + Nephew's Global Biostatistics group will conduct the statistical analysis for this study. Unless otherwise stated, all significance tests and hypothesis testing will be two-sided, performed at the 5% significance level. Resulting p-values will be quoted and 95% two-sided confidence intervals will be generated where appropriate. All p-values will be rounded to three decimal places, p-values less than 0.001 will be presented as '<0.001' in all tables.

Where data summaries are specified, categorical and ordinal variables will be summarized with frequencies and percentages. Continuous variables will be summarized with the following summary statistics: number of observations, mean, median, standard deviation, minimum and maximum values. All analyses will be performed in SAS 9.4 (or later).

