# Statistical Analysis Plan

A Multi-center Outcomes Clinical Study of the PyroTITAN™ HRA Shoulder Implant in Humeral Head Resurfacing

Number: CP-HRA-002  
ST: ST1159  
Version: 1.0 05/Oct/2023  
Page: 8 of 19

- **Safety Population (SAF)**, including all subjects who have received any study treatment.

All safety analyses will utilise the SAF Population. All non-safety related endpoints will be analysed using both the FAS and PP analysis populations.

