# Statistical Analysis Plan

A Multi-center Outcomes Clinical Study of the PyroTITAN™ HRA Shoulder Implant in Humeral Head Resurfacing

Number: CP-HRA-002  
ST: ST1159  
Version: 1.0 05/Oct/2023  
Page: 19 of 19

Events will be summarised by the AE/SAE/ADE/SADE/USADE classifications derived from the Investigator assessment of the event. In the case of disagreements, a separate summary of event classifications made by the Sponsor will also be provided.

In addition, AEs will be summarised by; severity (intensity), relationship to study device, relationship to procedure, outcome and duration of adverse event at trial discontinuation.

A listing will be provided which details subject number, AE description, start date, end date/ongoing, classification, severity, seriousness, relationship to device, relationship to procedure, anticipation, actions taken, outcome and whether study participation was discontinued due to the event.

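### SAP 7.12 summarises adverse events and device effects only as crude counts over all treated subjects, so effects outside the device-survival composite are understated if read as 5- or 10-year risks

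*SAP*

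**What the plan says.** SAP 7.12 summarises "The number of events and the number of subjects reporting: adverse events (AEs), serious adverse events (SAEs), adverse device effects (ADEs"), followed by serious and unanticipated serious device effects. The further breakdowns are by severity and by "relationship to study device, relationship to procedure, outcome and duration of adverse event at trial discontinuation". None of these uses time at risk. SAP 7.1 adds that "categorical and ordinal variables will be summarized with frequencies and percentages".

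The denominator follows from SAP 7.2. The safety population is defined as "including all subjects who have received any study treatment", and "All safety analyses will utilise the SAF Population". On missing data, SAP 7.3 says only that "Data will be analysed as observed in the study database".

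Follow-up is meant to last 10 years (Protocol 5.1), and SAP 6.1 expects it to be incomplete: "With an expected attrition rate of 10% per annum" for the original 150 subjects, and 10% lost to follow-up, with no period given, for the 237 added subjects. Subjects who withdraw after surgery need no further follow-up (Protocol 6.5). SAP 6.3 states that "A 5-year interim analysis will be carried out for this study", and SAP 7.14 explains that this allows the 2- and 5-year data to be published.

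The one analysis that allows for follow-up time is in SAP 7.9: Kaplan-Meier curves for device survival, with lost and withdrawn subjects censored, if the data permit.

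**The concern.** A subject who leaves in year 2 stays in the safety denominator for all ten years but can contribute events for only two. The proportion with an event is then lower than the 10-year risk, and the gap grows with the amount of loss and the lateness of the events.

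SAP 5.4 names infection, loss of fixation, breakage, dislocations and revisions as safety endpoints. Revisions fall inside the device-survival composite. The others do so only when they lead to replacement, removal or augmentation, or amount to chronic dislocation. Otherwise the crude count is all the SAP provides for them as adverse events.

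Protocol 11.2 intends to set the results against the literature. Crude percentages drawn from unequal follow-up do not support that comparison, and a reader of the published tables could take them for 5- or 10-year risks.

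**Working it through.** **Inputs.** From SAP 6.1: 150 original subjects with 10% attrition per year, and 237 added subjects with 10% lost to follow-up. From Protocol 5.1: 10 years of follow-up. Assumed here, because the documents give no figure: a true 10-year risk of 10%, a constant event hazard unless stated otherwise, and dropout independent of events.

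**The plan's own figures.** 150 × 0.9^10 = 52.3, matching the stated 52. Two-thirds of 52 is 34.7, matching about 35. 150 + 237 = 387, as stated.

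**Formula.** With event hazard λ and dropout hazard μ per year, the expected proportion of treated subjects with an observed event by year T is

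λ/(λ+μ) × [1 − exp(−T(λ+μ))].

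A 10% 10-year risk gives λ = −ln(0.9)/10 = 0.01054.

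**Original cohort (10% loss per year).**
- μ = −ln(0.9) = 0.1054, so λ/(λ+μ) = 1/11.
- Shown at 10 years: (1/11)(1 − 0.9^11) = (1/11)(0.6862) = 6.24%, against a true 10%.
- If each year's losses all fall at its start, the figure is 5.9%; if all at its end, 6.6%.
- At 5 years, the same hazard gives a true risk of 1 − 0.9^0.5 = 5.1%. Shown: (1/11)(1 − 0.9^5.5) = 4.0%.

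**Added cohort, if 10% is the 10-year total.** μ = −ln(0.9)/10 = λ. Shown: (1/2)(1 − 0.9^2) = 9.5%.

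**All 387.** (150 × 6.24% + 237 × 9.5%)/387 = 8.2%.

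**Event timing, at 10% loss per year and a true 10% risk.**

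| When the events occur | Calculation | Shown |
|---|---|---|
| All in year 1 | (1/2)(1 − 0.9^2) | 9.5% |
| All in years 0–2 | (1/3)(1 − 0.9^3) | 9.0% |
| Constant over 10 years | (1/11)(1 − 0.9^11) | 6.2% |
| All in years 5–10 | 0.9^5 × (1/6)(1 − 0.9^6) | 4.6% |
| All in year 10 | 0.9^9 × (1/2)(1 − 0.9^2) | 3.7% |

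**Check on the remedy.** In the original cohort under a constant hazard, expected time to event or dropout is 0.6862/(1.1 × 0.1054) = 5.92 years per subject. The rate is 0.0624/5.92 = 0.01054 per year, and 1 − exp(−10 × 0.01054) = 10.0%. Using time at risk therefore recovers the true value. Kaplan-Meier estimation does so without needing the constant hazard, provided dropout is independent of events.

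**The case against.** The strongest case on the other side has five parts.

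- **One attrition figure does not describe the study.** A reader might infer that a 10% risk would be shown as about 6% across the whole study. The documents do not support that. The 10% per year applies to 150 of 387 subjects. The other 237 (61%) have a different assumption with no period attached. This stands, and the size has to be given by cohort.
- **Many events come early.** Protocol 9.0 limits adverse events to those associated with the device or procedure, and Protocol 9.3 lists bleeding, clots, infection and swelling, which are largely perioperative. Such events would be understated only slightly. This also stands. It does not help with wear or loss of fixation, which Protocol 5.1 names as device-related; late timing is plausible for these, though the documents do not state it.
- **Some follow-up-adjusted analysis exists.** A reader might infer that the SAP has none for any safety item. SAP 7.9 contradicts that: revision, removal, complications needing replacement, removal or augmentation, and chronic dislocation all fall in the composite, whose Kaplan-Meier analysis censors losses. Radiographic performance is analysed under a separate SAP that is not among the documents. The gap is narrower for these reasons, but the Kaplan-Meier curves are conditional and effects outside the composite are not covered.
- **Two other mechanisms are weak.** Revised subjects leave the study (Protocol 7.0), but the revision is already counted and the removed implant can cause no new event, so this is unlike dropout. It is also tempting to say that 48 months of enrolment must make follow-up unequal at the 5-year interim. SAP 6.3 defines no data cut, so that cannot be settled.
- **The tables are descriptive.** Protocol 11.1 calls the study exploratory, and SAP 7.12 never labels its counts as 10-year risks. That is fair, but the plan gives no alternative from which those risks could be read.

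**Conclusion.** The point holds for adverse events and device effects outside the device-survival composite: SAP 7.12 gives only crude counts, and any loss to follow-up before an event makes the crude proportion fall short of the 5- or 10-year risk. With independent dropout the direction is clear; the size is not fixed by the documents.

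Under a constant hazard, a true 10% would show as about 6.2% in the original cohort, 9.5% in the added cohort if its loss is a 10-year total, and 8.2% overall. At 10% loss per year, event timing alone moves the shown figure from about 3.7% to 9.5%. The 10% true risk is illustrative. The primary endpoint analysis is not affected by this point. The change should be made, because a better method is available from dates the study already plans to use.

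**What to change.** Keep the raw counts and add to SAP 7.12:

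- Time-to-first-event cumulative incidence at 2, 5 and 10 years, with 95% confidence intervals and numbers at risk, for ADE, SADE and each of the five safety endpoints named in SAP 5.4. Subjects without the event are censored at last contact or last visit.
- A stated rule for how death and removal of the implant enter these estimates.
- Person-years of follow-up alongside the counts. Events per 100 person-years can be an optional supplement. They should not be the main summary, because a single rate assumes a constant hazard and spreads perioperative events over long follow-up.

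The data needed are already planned: adverse event start dates are in the SAP 7.12 listing, withdrawal dates go on the Withdrawal CRF (Protocol 10.0), and SAP 7.4 uses visit dates. Contact attempts with lost subjects are kept in source documents (Protocol 8.0), so last visit is the safer censoring date if last contact is not in the database.

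The cost is SAP wording and some extra tables: seven outcomes at three times is 21 estimates. The reported risks will be somewhat higher than the crude percentages.
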